CEUS will be performed on the same day of standard ultrasound evaluation of the carotid arteries using the same equipment. Preset contrast-specific modality (pulse inversion) is employed, adjusting image settings in order to maximize contrast signal visualization and using low mechanical index (0.08-0.12). Five ml of sodium hexafluoride (SonoVue, Bracco Imaging, Italy) were diluted 1:3 in saline. A 3 ml bolus is injected through a peripheral vein and then flushed with 5 ml saline. Plaque neovascularization will be assessed offline by 3 independent operators as previously described by Coli et al in 2008. Each lesion is graded as CEUS⁻ or CEUS⁺ depending on absence or presence of neovascularization signal, respectively. CEUS⁺ plaques were defined as plaques in which contrast bubbles, identified as moving bright spots, reached the plaque core or in which contrast signal was seen throughout the entire lesion. For each patient, the total number of neovascularized plaques will be recorded as a semi-quantitative index of neoangiogenetic activity.

Computed Tomography Angiography (CTA)

All patients will be examined with a 64-slice CT scanner (VCT Lightspeed, GE Healthcare, USA). Fifty ml of non-ionic, iso-osmolar contrast material (Iodixanol, 320 mg of iodine per millilitre, Visipaque 320; GE Healthcare, USA) prepared at 37°C will be injected into an antecubital vein through a 20 or 18-gauge catheter at a rate of 5 ml/s, followed by the injection 50 ml of saline. Contrast administration is performed using a dual-shot injector (Nemoto Kyorindo, Japan). The degree of stenosis in CCA, carotid bulb and ICA will be analyzed according to North American Symptomatic Carotid Endarterectomy Trial (NASCET) and ECST criteria. Briefly, for what concerns the NASCET method, the narrowest luminal area at the site of the stenosis and the area of normal artery distal to the plaque are measured, and the degree of stenosis was calculated as $[1 - (\text{narrowest area} / \text{normal area})] \%$. For the ECST, the method is analogous as for what is described above for duplex imaging, but areas are used instead of diameters. The axial data and multiplanar reconstruction (MPR) were used to determine the grade of stenosis, to calculate the plaque volume and the composition of the plaque, defined on the basis of plaque density in Hounsfield units (HU).

Brain magnetic resonance imaging

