Milan, 1st April 2012

Statistical plan for: Imaging della Placca Carotidea (IMPLAC) study

Funding: Italian Ministry of Health

Grant number: GR-2009-1608780

NCT number: NCT03333330

The primary outcome of the study will be the presence of white matter hyperintensities (WMH) progression (defined as the appearance of at least 1 new lesion on cerebral magnetic resonance imaging) after 18 months. The secondary endpoint will be the reduction of brain volumes (total volume, grey matter volume and white matter volume) at 18 months. Our primary analysis will be focused at identifying independent predictors of WMH among clinical characteristics of the patients as well as plaque related variables, including volumetric measures of plaque volumes and characteristics of plaque vulnerability, such as presence of ulcer or neovascularization. All continuous variables will be tested for normality using Shapiro-Wilk normality test and are expressed as mean±standard deviation (SD) or median [interquartile range (Q1-Q3)] as appropriate. Categorical variables are summarized as absolute frequency (percentage). Group differences will be tested using unpaired t test, Mann-Whitney U test or Wilcoxon matched pair signed rank test. Spearman's rank correlation coefficient was used to assess statistical dependence. Association between categorical variables was tested using Chi-squared test or Fisher's exact test as appropriate. A $p<0.05$ was considered significant. A multivariate regression analysis was then performed to identify factors that independently influence the burden of WMH in terms of number and volume. All variables associating to WMH burden with a $p<0.10$ will be included in the multivariable model. Our main hypothesis is that subjects with a high plaque burden will experience the highest progression of WMH. We calculated the sample size for multivariate logistic regression analysis with a power of 0.8 and an alpha of 0.05. We will analyze the highest tertile of carotid plaques burden in terms of plaque volume versus others (see Sillesen, 2012). By this definition, the prevalence of high burden atherosclerosis will be 33%. We estimated a clinically relevant probability of progressing in terms of WMH in the high burden group to be 50%, while subjects without high burden plaques are estimated to progress in terms of WMH as the general population with carotid atherosclerosis in a similar time frame. This probability would be estimated to be around 15% (see Dufoil, 2005 and Pico, 2002). The estimated sample size would be 58 individuals. All statistical analyses will be performed using GraphPad Prism 5 (GraphPad Software Inc., La Jolla, USA), IBM SPSS Statistics 20 (IBM, Armonk, USA) or R v3.1.2.

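### Should the main hypothesis be tested with plaque volume as a continuous term instead of top tertile versus the rest?

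*SAP*

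**What the plan says.** The Protocol, under Computed Tomography Angiography (CTA), uses the axial and reconstructed images "to calculate the plaque volume and the composition of the plaque", so a quantitative plaque volume is available for each participant.

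The SAP, a single undivided section, uses that volume in two places.

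- **Main hypothesis and sample size.** The hypothesis reads: "Our main hypothesis is that subjects with a high plaque burden will experience the highest progression of WMH". The next sentence reads: "We calculated the sample size for multivariate logistic regression analysis with a power of 0.8 and an alpha of 0.05". The exposure follows: "We will analyze the highest tertile of carotid plaques burden in terms of plaque volume versus others". The SAP puts the share in the high-burden group at 33% and its progression risk at 50%. For the rest, "subjects without high burden plaques are estimated to progress in terms of WMH as the general population with carotid atherosclerosis", taken as about 15%. The result is 58 individuals.
- **Primary analysis.** This is described as a search for independent predictors among clinical and plaque variables, "including volumetric measures of plaque volumes and characteristics of plaque vulnerability". Variables associated with WMH burden at p<0.10 go into the multivariable model. Here the SAP does not say whether volume enters as the tertile, as raw volume or as log volume.

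**The concern.** Two things invite criticism. First, cutting a continuous measurement at a tertile discards the ordering within each group. The 50% and 15% are only group averages, so they fit a gradual rise as well as a jump at the cut. If the rise is gradual, the split gives up power that data already collected could supply.

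Second, the predictor list leaves the form of volume open. Only about 15 progressors are expected, and an analyst who tried several forms and reported the best would have more than the nominal chance of a false positive. A wording change that needs no new data seems an easy remedy for both.

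**Working it through.** **1. Reproduce the 58.** Inputs from the SAP: share exposed B = 0.33, risk in the exposed P2 = 0.50, risk in the others P1 = 0.15, alpha 0.05, power 0.80. Two-sided testing is assumed, because it reproduces the figure. The formula for logistic regression with one binary covariate is

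N = [z(0.975)·√(P(1−P)/B) + z(0.80)·√(P1(1−P1) + P2(1−P2)(1−B)/B)]² / [(P2−P1)²(1−B)]

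- Overall risk P = 0.67×0.15 + 0.33×0.50 = 0.2655, so expected progressors are 58×0.2655 = 15.4.
- First term: 1.960×√(0.1950/0.33) = 1.507.
- Second term: 0.842×√(0.1275 + 0.5076) = 0.671.
- N = (1.507 + 0.671)² / (0.1225×0.67) = 4.741/0.0821 = 57.8, rounded up to 58.

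The stated size is right for the tertile contrast.

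**2. Power at 58, continuous term against tertile term.** Logistic model without covariates, likelihood-ratio test, 19 of 58 in the top tertile, 40,000 simulations, every scenario calibrated to 50% versus 15%. In the graded case the logit of risk is linear in a normally distributed volume scale (intercept −1.286, slope 1.196 per SD, odds ratio 3.31). That implies risks of about 8%, 22% and 50% by third. The 8% and 22% are assumptions and are not in the SAP.

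| Shape of risk | Continuous | Tertile | Difference (points) |
|---|---|---|---|
| Graded | 93.7% | 78.2% | +15.5 |
| Half graded, half step | 81.0% | 79.1% | +1.9 |
| 40% graded, 60% step | 77.4% | 78.7% | −1.3 |
| Step at the sample tertile | 62.0% | 79.4% | −17.4 |
| Step at a fixed population cut | 62.1% | 69.6% | −7.5 |

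Break-even lies at a graded share between 0.4 and 0.5.

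**3. Sensitivity to the assumptions.**

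- *Scale.* If volume is log-normal (log-SD 1) and entered raw while risk is linear in log volume, the graded case becomes 86.8% against 78.6% (+8.2). With a step at the sample tertile it is 49.9% against 79.4% (−29.5).
- *One covariate correlated with volume, no effect of its own (assumed).* Correlation 0.3: 91% against 74% graded, 58% against 78% step. Correlation 0.5: 86% against 64%, and 51% against 73%. Correlation 0.7: 72% against 44%, and 39% against 65%.
- *52 analysed (10% loss, assumed), no covariate.* 91.2% against 75.4% graded; 57.7% against 77.1% step.

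Every pair shows a gain under one shape and a loss of similar or greater size under the other.

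**4. False positives if the form were chosen after seeing results.** No true association, n = 58, log-normal volume with log-SD 1.

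| Test | Tertile alone | Better of log and tertile | Best of log, raw and tertile |
|---|---|---|---|
| Likelihood ratio | 5.9% | about 9% | about 11% |
| Wald | 3.6% | about 6% | about 7% |

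The SAP does not name the test. Part of the distance from 5% to 9% is the small-sample behaviour of the likelihood-ratio test, which is already above 5% with a single prespecified form.

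**The case for a change.** The best case for a change rests on false positives, because that argument does not depend on the shape of risk. The SAP lists rank correlation and two-group tests, which suit continuous volume, beside chi-squared and Fisher tests, which suit the tertile. Any version of volume that passes p<0.10 could enter the model. With about 15 progressors, choosing among forms adds roughly 3 to 5 points to the error rate, and naming one form would remove that at the cost of a sentence.

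Part of this stands: the predictor list does not give the form, and choosing after the fact would inflate error under either test. But the inflation arises only if the analyst sets aside the form that the SAP does state. For the main hypothesis the exposure, the split, the model, the alpha and the sample size are all given together. The argument also does not favour a continuous term, since fixing either form would do, and one is already fixed where it matters most.

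The power argument stands only conditionally. A sponsor who expects a gradual rise could reasonably prefer a continuous term. The planning assumptions, with the top group at 50% and everyone else at a background rate, are at least as compatible with a threshold. The SAP cites an outside source for the tertile, and its merits cannot be judged from these documents.

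**Conclusion.** No change follows. Continuous volume against the tertile is a fair trade-off: about 16 points of power gained if risk is graded, about 17 lost if it steps at the sample tertile, and near equality for an even mixture. These figures assume 58 analysed, no covariates, likelihood-ratio tests and a normal volume scale. Adding a correlated covariate, losing 10% or entering raw volume changes the sizes but not the two-sided nature of the choice. The documents give neither the shape of risk nor the distribution of volume, so neither form can be shown to be better, and the split is the contrast for which 58 is correct.

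The unstated form in the predictor list is a small gap in detail. The sensible reading carries the tertile from the main hypothesis into the logistic model and treats continuous volume as supportive. Giving the cut-point in volume units when results are reported would help readers, but that is a matter of reporting.
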